6.5. Concomitant Therapy

For Part G, concomitant therapy with fulvestrant is permitted.

No other chemotherapy, immunotherapy, or experimental medications are permitted while the patients are on this study. Hormone replacement therapy initiated before study entry may be continued but should be considered for discontinuation. Palliative radiotherapy, unless required due to progressive disease, is permitted during the study. Disease progression requiring specific antitumor therapy will necessitate early discontinuation from the study. Appropriate documentation for all forms of premedications, supportive care, and concomitant medications must be captured for each cycle on the case report form.

Patients should receive full supportive care during this study.

Growth factors may be administered in accordance with American Society of Clinical Oncology (ASCO) guidelines, if clinically indicated (Smith et al. 2015; Rizzo et al. 2010). See [Table JPBA.6.2](#) for dose adjustments and delays related to administration of growth factors.

Transfusion therapy is permitted during this study.

Modulators of CYP3A

LY2835219 is extensively metabolized through oxidation by CYP3A. In clinical drug interaction studies,

- coadministration of clarithromycin, a strong CYP3A inhibitor, increased exposure (AUC) of LY2835219 by 3.4-fold (Study I3Y-MC-JPBE), and
- coadministration of rifampin, a strong CYP3A inducer, decreased exposure of LY2835219 by 95% (Study I3Y-MC-JPBF).

Strong inhibitors of CYP3A (given via non-topical routes of administration) should be substituted or avoided if possible ([Attachment 8](#)). This includes grapefruit or grapefruit juice. In particular, avoid oral administration of the very strong CYP3A inhibitor, ketoconazole.

If coadministration with a strong CYP3A inhibitor is unavoidable, investigators should reduce the dose of LY2835219 by 50 mg at the start of CYP3A inhibitor treatment. That is, for patients receiving 150 mg twice daily, reduce the dose to 100 mg twice daily. For patients who have already dose reduced to 100 mg twice daily for tolerability, reduce the dose further to 50 mg twice daily. Alternatively, the investigator may consider suspending LY2835219 for the duration of the CYP3A inhibitor medication. Dose suspensions ≥ 28 days must be discussed with Lilly CRP/CRS.

Upon discontinuation of the strong CYP3A inhibitor, the dose of LY2835219 may be re-escalated to the dose that was used before starting the strong inhibitor after a sufficient washout period (3-5 half-lives of the strong inhibitor). Re-escalation of the LY2835219 dose requires review and approval from Lilly CRP/CRS.

Inducers of CYP3A should be substituted or avoided if possible ([Attachment 8](#)).

Coadministration with a CYP3A inducer ≥ 28 days must be discussed with Lilly CRP/CRS.

Transporter Substrates

At clinically relevant concentrations, LY2835219 inhibits the transporters P-glycoprotein, breast cancer resistance protein, organic cation transporter 2 (OCT2), multidrug and toxin extrusion protein 1 (MATE1), and MATE2-K. The observed serum creatinine increase in clinical studies with LY2835219 is likely due to inhibition of tubular secretion of creatinine via OCT2, MATE1, and MATE2-K. In vivo interactions of LY2835219 with narrow therapeutic index substrates of these transporters, such as digoxin and dabigatran, may occur.

6.5.1. *Supportive Management for Diarrhea*

In the event of diarrhea while a patient is receiving LY2835219, supportive measures should be initiated as early as possible. These include the following:

- At the first sign of loose stools, the patient should initiate anti-diarrheal therapy (for example, loperamide), and notify the investigator for further instructions and appropriate follow-up.
- Patients should also be encouraged to drink fluids (for example, 8 to 10 glasses of clear liquids per day).
- Site personnel should assess response within 24 hours.
- If diarrhea does not resolve with anti-diarrheal therapy within 24 hours to at least Grade 1, then dosing should be suspended until diarrhea is resolved to at least Grade 1.
- When LY2835219 recommences, dosing should be adjusted as outlined in [Table JPBA.6.2](#).

For severe cases of diarrhea, the measurement of neutrophil counts, body temperature, and the proactive management of diarrhea with antidiarrheal agents should be considered.

If diarrhea is severe (requiring IV rehydration) and/or associated with fever or severe neutropenia, broad-spectrum antibiotics such as fluoroquinolones should be considered.

Patients with severe diarrhea or any diarrhea associated with severe nausea or vomiting should be carefully monitored and given IV fluid (IV hydration) and electrolyte replacement as clinically indicated.

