In addition, PK/PD modeling suggested that AUC levels associated with tumor growth delay in preclinical *in vivo* efficacy studies (approximately 3600 to 9500 ng·hr/mL) should be reached in patients within a dose range of 300 to 700 mg administered once daily ([Table JPBA.4.3](#)). Based on the *steady-state exposures* observed at the Not Severely Toxic Dose in rats and the highest Minimally Toxic Dose in dogs, the median exposure multiples predicted at steady state for this clinical dose range were approximately 8 to 18 and 0.3 to 0.7, respectively.

During the dose escalation phase, preliminary analysis of PK data from the initial 4 dose levels (50, 100, 150, and 225 mg every 24 hours) indicated less than dose-proportional increases in exposure. Based on these results, a twice daily schedule was introduced in Part A with LY2835219 administered orally at the following planned dose levels: 75, 100, 150, 200, 275, 350, and 450 mg every 12 hours for 28 days. Importantly, the first planned dose level (75 mg every 12 hours) corresponded to a daily dose of 150 mg, which was 1 dose level lower than that of the highest previously explored dose level (225 mg every 24 hours). For the twice daily schedule, the highest dose of LY2835219 evaluated was 275 mg every 12 hours. At this dose level, 2 of the 3 patients experienced DLT of Grade 3 fatigue. At the next lower dose level of 200 mg every 12 hours, 1 of the 7 patients also experienced DLT of Grade 3 fatigue. Therefore, the maximum tolerated dose (MTD) was established at 200 mg every 12 hours.

During the tumor-specific expansion phases, patients initially received LY2835219 at the MTD of 200 mg every 12 hours. A preliminary interim safety review with data from 56 patients indicated that 29 patients experienced diarrhea possibly related to study drug: 17 Grade 1 (30%), 9 Grade 2 (16%), 3 Grade 3 (5%), none Grade 4 (0%), and none Grade 5 (0%). Based on the frequency of Grade 1/2 diarrhea and the observation of clinical activity at doses below the MTD, the initial starting dose was changed to 150 mg every 12 hours with JPBA amendment (f) to gain additional PK data and clinical experience around safety/tolerability. Importantly, diarrhea experienced by patients is manageable with standard anti-diarrheal agents. Therefore, early treatment with anti-diarrheal agents (e.g., loperamide) is recommended and the initial starting dose will return to the MTD of 200 mg every 12 hours with JPBA amendment (g).

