6.2.3. Dose Confirmation Phase (Parts B, C, D, E, F, and G)

After the MTD has been identified in Part A, at least 15 and up to 45-60 patients will be enrolled in each of the 6 tumor-specific expansions: Part B (non-small cell lung cancer), Part C

(glioblastoma multiforme), Part D (breast cancer), Part E (melanoma), Part F (colorectal cancer), and Part G (HR+ breast cancer).

During the dose confirmation phase, patients may enroll concurrently and will be treated at a dose no greater than the MTD (200 mg every 12 hours). Patients enrolled under JPBA amendment (f) who are still receiving LY2835219 at a dose of 150 mg every 12 hours may, at the discretion of the investigator, be escalated to 200 mg every 12 hours. Patients enrolled under JPBA amendment (g) or subsequent amendment should initially receive LY2835219 at a dose of 200 mg every 12 hours. For all patients, dose adjustments are permitted as outlined in Section 6.2.4.1.

If DLT-equivalent toxicities occur in 33% or more of patients within a tumor-specific cohort expansion, then investigators and the Lilly CRP will assess the nature and severity of these toxicities. No additional patients will be accrued until this safety review is completed and a decision is made either to continue at the current dose or to deescalate the dose and define a new dose for the expansion phase. The safety review and decision will be documented in writing.

During the dose confirmation phase, paired tumor biopsies should be obtained, whenever clinically feasible, before (Day -14 to Day -4) and after (Day 8 to Day 22) administration of study drug in Cycle 1.

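### Section 6.5's flat 50 mg cut for a strong CYP3A inhibitor leaves a 200 mg Q12H patient at about 2.55 times the parent AUC at the MTD, by the protocol's own 3.4-fold figure

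*Protocol*

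**What the plan says.** Protocol Section 6.5 (Modulators of CYP3A) first asks sites to substitute or avoid strong inhibitors. If one is unavoidable, "investigators should reduce the dose of LY2835219 by 50 mg at the start of CYP3A inhibitor treatment". Two examples follow. The first reads "That is, for patients receiving 150 mg twice daily, reduce the dose to 100 mg twice daily". The second, for patients already lowered to 100 mg for tolerability, says to "reduce the dose further to 50 mg twice daily". There is no example for 200 mg. Suspension is offered as an option: "Alternatively, the investigator may consider suspending LY2835219 for the duration of the CYP3A inhibitor medication".

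The same section gives the size of the interaction: "coadministration of clarithromycin, a strong CYP3A inhibitor, increased exposure (AUC) of LY2835219 by 3.4-fold".

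On dosing in the expansion parts, Section 6.2.3 says that patients enrolled under amendment (g) or later "should initially receive LY2835219 at a dose of 200 mg every 12 hours", and that patients "will be treated at a dose no greater than the MTD (200 mg every 12 hours"). Table JPBA.6.3 lists 200 mg Q12H as dose level 0. Section 4.7 reports on 275 mg Q12H, the highest twice-daily dose given in Part A: "At this dose level, 2 of the 3 patients experienced DLT of Grade 3 fatigue". Under Section 6.2.2, more than one DLT at a dose level means that the MTD has been exceeded.

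**The concern.** A fixed 50 mg cut removes a quarter of a 200 mg dose, while the interaction reported beside it more than triples parent AUC. The cut therefore falls far short of the rise at exactly the dose on which current patients start. Because the examples begin at 150 mg, a site with a patient at 200 mg has only the general sentence to follow, and that sentence gives 150 mg.

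Safety and tolerability are the primary objective, and the MTD was set by tolerability in Part A. A site that follows the reduction option could expose a patient to avoidable toxicity. Section 6.5 asks for contact with the sponsor's physician for suspensions of 28 days or more and for re-escalation, but not before starting a strong inhibitor together with 150 mg Q12H. Amendment (j) revised this part of Section 6.5 (Section 4.4), so this is current text.

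**Working it through.** **Inputs**
- AUC ratio with a strong inhibitor: 3.4 (Section 6.5, clarithromycin), read as with/without inhibitor.
- Cut: 50 mg per dose (Section 6.5).
- MTD and starting dose: 200 mg Q12H (Sections 4.7 and 6.2.3).
- Level that exceeded the MTD: 275 mg Q12H, 2 of 3 patients with a DLT (Section 4.7).

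The protocol states no net exposure after the cut, so there is no plan figure to reproduce. The flat cut does reproduce both worked examples (150 − 50 = 100; 100 − 50 = 50), so 200 − 50 = 150 is the consistent reading.

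**Net parent AUC, assuming AUC proportional to dose**

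Equivalent dose = 3.4 × reduced dose; multiple of the MTD level = equivalent dose / 200.

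| Step (mg Q12H) | Equivalent dose (mg Q12H) | Multiple of MTD level | Relative to 275 mg |
|---|---|---|---|
| 200 to 150 | 3.4 × 150 = 510 | 2.55 | 510/275 = 1.85 |
| 150 to 100 | 3.4 × 100 = 340 | 1.70 | 340/275 = 1.24 |
| 100 to 50 | 3.4 × 50 = 170 | 0.85 | 170/275 = 0.62 |

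The first row also exceeds 450 mg Q12H, the highest level planned in Table JPBA.6.1.

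**How weak must the inhibitor be?** From 200 mg, the cut keeps parent AUC at or below the MTD level only if the ratio is at most 200/150 = 1.33. It passes the 275 mg level above 275/150 = 1.83. The documents give no ratio for other listed inhibitors, so a range of assumed ratios at 150 mg is shown: 1.5 gives 225 mg equivalent, 2 gives 300, 2.5 gives 375 and 3.4 gives 510.

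**Sensitivity of the 2.55**
- Predicted AUCs in Table JPBA.4.3 for 300 and 400 mg/day: (2,700/3,650) × 3.4 = 2.52.
- Section 4.7 reports less than dose-proportional exposure at 50 to 225 mg once daily but gives no exponent. With AUC proportional to dose^b and b assumed, the multiple is 3.4 × 0.75^b: 2.62 at b = 0.9, 2.70 at 0.8, 2.78 at 0.7, with a limit of 3.4 as b falls to 0. Sub-proportionality makes the multiple larger.
- If an increase by 3.4-fold is taken literally as 4.4 times: 0.75 × 4.4 = 3.30.

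**Dose that holds parent AUC at the MTD level:** 200/3.4 = 58.8, about 59 mg Q12H. This depends on proportionality. It falls to about 51 mg at b = 0.9 and about 43 mg at b = 0.8.

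**The case against.** The strongest objection is that parent AUC is not total active exposure. The drug is cleared by CYP3A oxidation and the trial assays three metabolites (Section 7.2.1), whose levels an inhibitor may also change. The documents give neither the metabolites' activity nor their change under inhibition. The 3.4-fold figure also comes from one study with one inhibitor. This stands. A reader might infer 2.55 times the total drug exposure at the MTD, but the documents support that figure only for parent AUC with an inhibitor of clarithromycin's strength.

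Three other stronger readings do not hold:
- A reader might infer that the rule breaches the Section 6.2.3 cap at the MTD. That cap is on nominal dose, and 150 mg complies. No exposure ceiling is stated.
- A reader might infer that interaction toxicity would be booked against a 150 mg dose group. SAP Sections 6.3.1 and 6.3.5.2 summarize expansion adverse events by tumor-specific cohort, not by dose received. Reduced doses and concomitant medications are reported too (SAP 6.3.4 and 6.3.3.3).
- A reader might link the fluoroquinolone advice in Section 6.5.1 to ciprofloxacin in Attachment 8 and infer a built-in route to this rule. Ciprofloxacin is the only fluoroquinolone listed there. Choosing an unlisted antibiotic satisfies both sections, so it is not shown to be unavoidable.

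It is also fair to say that the 275 mg comparator rests on 3 patients (2/3, Clopper-Pearson 95% CI 9.4% to 99.2%) and that 510 mg extrapolates beyond any Q12H dose given. Even so, the protocol's own rule classes 275 mg as exceeding the MTD. Avoidance comes first, suspension is available, and Table JPBA.6.2 requires suspension, reduction or discontinuation for specified toxicities. These make the situation rarer or respond after toxicity appears. They do not correct the dose that the reduction option prescribes.

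**Conclusion.** The concern holds for parent AUC. Followed as written, the reduction option takes a 200 mg Q12H patient to 150 mg Q12H. With a 3.4-fold rise and dose-proportional AUC, that is about 2.55 times the parent AUC at the MTD. Less than proportional kinetics would raise the multiple. The 150 to 100 mg step has the same problem at 1.70 times. The 100 to 50 mg step does not, at 0.85 times under proportionality. How far metabolites offset the rise, how strong the other listed inhibitors are and how many patients take one are all unknown from the documents, so no patient count or toxicity rate is claimed.

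**What to change.** At the next amendment, revise the paragraph in Section 6.5:
- State the 200 mg Q12H case explicitly.
- For patients at 200 mg or 150 mg Q12H, make suspension for the duration of the strong inhibitor the default.
- Allow continued dosing only after consultation with the sponsor's physician, at a reduced dose supported by the Study I3Y-MC-JPBE parent and metabolite data. On parent AUC alone and under proportionality, about 59 mg Q12H or less stays within the MTD level. The 50 mg Q12H that Section 6.5 already names would meet this, but with little margin if exposure is less than proportional, so the dose should rest on those data.
- Leave the 100 to 50 mg step in place.

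The cost is one paragraph and a notice to sites, with no new data collection and no change to sample size or SAP. The downside is some missed doses during inhibitor treatment.

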6.6. Treatment Compliance

Patient compliance with study medication will be assessed at each visit by review of the patient diary, direct questioning, and counting of returned solid oral dosage units. Deviation(s) from the prescribed dosage regimen should be recorded on the Case Report Form (CRF).

The patient must take $\geq 75\%$ of the planned doses in a cycle to be deemed compliant with study drug administration. Similarly, a patient may be considered noncompliant if he or she is judged by the investigator to have intentionally or repeatedly taken more than the prescribed amount of medication. Any missed doses during a cycle will be omitted and not replaced. In the event of a missed dose, a patient should resume and continue dosing beginning with the next scheduled dose. Potential discontinuation of a patient due to study drug noncompliance will be discussed between the investigator and the Lilly CRP before making the final determination for discontinuation. If a patient is discontinued due to study drug noncompliance, the patient may be replaced.

7. Safety, Pharmacokinetic, Pharmacodynamic, and Efficacy Data Collection

7.1. Safety Evaluations

The safety and tolerability of LY2835219 have been assessed in nonclinical toxicology studies and the results from these studies are detailed in the IB. This Phase 1 study contains a detailed safety monitoring plan that will permit initial characterization of the safety profile of LY2835219 in patients. Study procedures and their timing, including tolerance limits for timing, are described in the Study Schedule ([Attachment 1](#)).

Blood samples and ECGs will be collected at the times specified in the Study Schedule ([Attachment 1](#)). Laboratory tests including hematology, chemistry, and special blood tests will be performed. A serum pregnancy test will be administered to females with child bearing potential. [Attachment 2](#) lists the specific laboratory tests that will be performed for this study. Enrollment and treatment decisions may be based upon results of tests performed locally. If local laboratory tests are used for this purpose, then a duplicate specimen must be submitted to the central laboratory. Discrepancies between local and central laboratory and ECG results that may have an impact on eligibility or treatment decisions will not be considered protocol violations. When both a local and central laboratory result are obtained and there is a discrepancy in these laboratory values, the local laboratory values will be used for determining a DLT, after discussion with the study investigator(s).

Samples collected for specified laboratory tests will be destroyed within 60 days of receipt of confirmed test results. Certain samples may be retained for a longer period, if necessary, to comply with applicable laws, regulations, or laboratory certification standards.

If a patient's dosage is reduced or treatment discontinued as a result of an AE, study-site personnel must clearly report to Lilly or its designee via CRF the circumstances and data leading to any such dosage reduction or discontinuation of treatment.

All concomitant medications should be recorded throughout the patient's participation in the study, until conclusion of the study follow-up period.

7.1.1. Safety Data Collection and Review

Investigators are responsible for monitoring the safety of patients who have entered into this study and for alerting Lilly or its designee to any event that seems unusual, even if this event may be considered an unanticipated benefit to the patient. The investigator is responsible for the appropriate medical care of the patient during the study.

The investigator, monitor, and sponsor will review the collected data regularly for evidence of AEs. All patients will be assessed routinely for AEs as outlined in the study schedule. All AEs observed on study will be graded using the Common Terminology Criteria for Adverse Events (CTCAE [CCI](#))

The investigator remains responsible for following, through an appropriate health care option, all AEs that are SAEs or that caused the patient to discontinue before completing the study. The

patient should be followed until the event is resolved, the event is no longer considered to be drug-related, the event becomes stable or returns to baseline, a new treatment is initiated for the patient, or the patient dies or is lost to follow-up. Frequency of AE and SAE follow-up evaluation is left to the discretion of the investigator.

Investigators or their designees must document their review of each laboratory report.

This study requires ECG monitoring at both baseline and prespecified time points (see [Attachment 1](#)). For each subject 12-lead digital ECGs will be obtained as single ECGs according to the Study Schedule ([Attachment 1](#)). Subjects must be supine for approximately 5 to 10 minutes before ECG collection and remain supine during ECG collection. ECGs may be obtained at additional times, when deemed clinically necessary. Collection of more ECGs than expected at a particular time point is allowed when needed to ensure high quality records.

ECGs will be interpreted by a qualified physician (the investigator or qualified designee) at the site as soon after the time of ECG collection as possible, and ideally while the subject is still present, to determine whether any clinically relevant findings are present.

After enrollment, if a clinically significant increase in the QTcB interval from baseline, or other clinically significant quantitative or qualitative change from baseline, is present, the investigator will assess the subject for symptoms (for example, palpitations, near syncope, syncope) and to determine if the subject can continue in the study. The investigator or qualified designee is responsible for determining if any change in subject management is needed and must document his/her review of the ECG printed at the time of evaluation.

All digital ECGs will be electronically transmitted to a central ECG laboratory designated by Lilly. A cardiologist at the central ECG laboratory will then conduct a full overread on the ECG (including all intervals); a report based on data from this analysis will be issued to the investigative site.

It is recognized that ECG interpretations by the investigator (or qualified designee) and by the cardiologist at the central ECG laboratory may be different. When there are differences in ECG interpretation between the investigator (or qualified designee) and the cardiologist at the central ECG laboratory, the interpretation of the investigator (or qualified designee) will be used for study entry and immediate subject management. Interpretations from the cardiologist at the central ECG laboratory will be used for data analysis and report writing purposes.

The investigator (or qualified designee) must document his/her review of the ECG printed at the time of evaluation, the final over-read ECG report issued by the central ECG laboratory, and any alert reports.

